# 7.2. Scientific Rationale for Study Design

This study is designed to evaluate the safety of APL-9 in subjects with respiratory failure due to COVID-19, the disease caused by SARS-CoV-2 infection. Secondary objectives include

assessments of efficacy of APL-9 (evaluating survival, length of hospital admission, and lung function), APL-9 PK results, and the effect of APL-9 on complement activation biomarkers.

This study is being executed during a worldwide outbreak of COVID-19 that has resulted in capacity issues at many medical facilities. Additionally, the highly contagious nature of COVID-19 (compounded by a shortage of personal protective equipment) has caused concerns about the safety of health care providers caring for these seriously sick patients. Consequently, this study is designed to minimize any additional burden on clinical sites, including minimizing the number of assessments and interventions that the study will require in addition to SOC, while still ensuring the safety of subjects.

The first portion of this 2-part study will entail initial DMC review and confirmation of product safety in 6 subjects under open-label treatment conditions. The second part will be a doubleblind, vehicle-controlled comparison of safety and efficacy. The investigational product (APL-9 in saline vehicle for infusion) and reference product (vehicle control) will be prepared by unblinded pharmacists and will be indistinguishable to blinded study personnel to limit bias in study assessments. Either APL-9 or vehicle control will be administered as add-on therapy to SOC. Most interventions and assessments may be accomplished in conjunction with SOC, without requiring additional hospital visits or resources.

Subjects with active bacterial, fungal, or parasitic infection are excluded, and enrolled and treated subjects will also receive treatment with a broad-spectrum antibiotic to prevent the theoretical risk of bacterial infections due to complement inhibition. A DMC will conduct periodic reviews of safety and efficacy data to ensure the safety of study subjects and to advise the sponsor on futility.

# 7.3. Justification for Dose

A single bolus infusion of 180 mg of APL-9 followed by continuous infusion of 360 mg/day will be tested in this study. This will result in an initial dose of 540 mg of APL-9 in the first 24 hours of dosing (followed by 360 mg/day on all subsequent days). This dose and higher doses were well tolerated in a previous study in healthy volunteers and demonstrated comparable PK and complement inhibition to that in prior cynomolgus monkey studies. More detailed information can be found in the APL-9 Investigator's Brochure.

The purpose of this dosing scheme is to achieve rapid complement inhibition by APL-9 upon initiation of treatment, followed by a regimen selected to keep the complement system consistently suppressed for the duration of study drug administration. Discontinuation of dosing is expected to restore normal complement activity within 24 hours.

[figure not shown]

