# 5.3. Benefit-Risk Assessment

This is an interventional study in COVID-19 subjects with respiratory failure, including mild to moderate ARDS, a life-threatening complication of SARS-CoV-2 infection. Based on the known pathological role of complement overactivation in ARDS, C3 inhibition by APL-9 may improve pulmonary function in subjects with COVID-19. If efficacious, APL-9 may also reduce COVID-19-associated morbidity and mortality and shorten the length of stay in intensive care and respiratory units, which may be in critical shortage during outbreaks.

Nonclinical studies of SARS-CoV-1 have indicated that complement inhibition had beneficial effects to reduce lung inflammation, and a healthy volunteer clinical study of IV APL-9, a C3 inhibitor, demonstrated acceptable PK and safety profiles. Subjects participating in this study will also receive SOC therapy independent from randomization.

The risks include local adverse effects from IV dosing, adverse effects that are currently unknown, additional infections secondary to COVID-19, possible increased risk of bacterial infection due to complement inhibition, and possible lack of efficacy. All subjects who are to receive study drug treatment will also receive a broad-spectrum antibiotic (see Section 9.5) to counter the theoretical concern of increased risk of bacterial infection due to complement inhibition. As a further subject safety mechanism, the study will initially enroll and treat 6 subjects in an open-label fashion with APL-9 (Part 1). A data monitoring committee (DMC) will review the clinical data collected in Part 1 before Part 2 of the study will be initiated. Required criteria for initiation of Part 2 will include (1) no fatal/life-threatening serious adverse events (SAEs) thought possibly related to APL-9 by the DMC, and (2) no more than 1 subject requiring premature treatment discontinuation by the investigator due to adverse events (AEs) or abnormal laboratory tests. After Part 2 is initiated, the DMC will perform further reviews of clinical data after the 10th and 30th subjects have reached the approved treatment duration, discontinuation of respiratory support (oxygen supplementation or mechanical ventilation), or hospital discharge, whichever occurs latest.

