## 6.2. Endpoints

## 6.2.1. Primary Objective Endpoint

• Cumulative incidence of treatment-emergent SAEs and treatment-emergent adverse events (TEAEs)

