## Part 2 (Randomized Double-Blind Period):

Part 2 of the study will be initiated only upon recommendation from the DMC. Required criteria for initiation of Part 2 will include (1) no fatal/life-threatening SAEs thought possibly related to APL-9 by the DMC, and (2) no more than 1 subject requiring premature treatment discontinuation by the investigator due to AEs or abnormal laboratory tests. All subjects will receive SOC independent of their randomization. Approximately 60 subjects will be randomly

assigned in a 1:1 ratio to blinded treatment with either APL-9 or saline vehicle. Subjects will receive treatment with APL-9 or vehicle from Day 1 through Day 7, discontinuation of respiratory support (supplemental oxygen or mechanical ventilation), or hospital discharge, whichever occurs latest.

Subjects may receive treatment beyond Day 7 if the DMC approves an extended treatment duration following the review of data from Part 1 or during the conduct of Part 2. The DMC may approve any extended treatment duration up to and including Day 21; extended treatment will be allowed only in subjects who still require respiratory support (oxygen supplementation or mechanical ventilation) at Day 7 with an improved PaO2/FiO2 ratio of at least 20 mm Hg from baseline if arterial blood gas (ABG) test results are available for comparison. If ABG test results are not available, an improvement in FiO2 of at least 4% in nonventilated patients (eg, those on nasal cannula) and 10% in mechanically ventilated patients is needed. FiO2 should be weaned following the site's protocol to keep oxygen saturation at 89% or above. Treatment beyond Day 7 and through any DMC-approved extension will be at the discretion of the investigator. Treatment beyond Day 7 and up to and including any DMC-approved extension will be at the discretion of the investigator.

Follow-up safety assessments for each subject will be collected 30 days following the last dose of study treatment (up to and including Study Day 51 with a +7-day window). Safety assessments may be performed any time during the 30-day follow-up period at the investigator's discretion but are required 30 days after the last dose of study drug (up to and including Study Day 51 with a +7-day window). These assessments will be conducted via inpatient assessment (for subjects still hospitalized) or by telephone call (for subjects discharged).

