## 12.4. Safety Analysis

All safety analyses will be summarized for the safety set.

Adverse events will be coded using MedDRA. All AEs, including TEAEs, will be summarized by System Organ Class, Preferred Term, and treatment group for number of subjects and proportion reporting the event. A similar summary will be produced for SAEs, AEs leading to termination, severe AEs, and AEs related to the investigational product. The intensity of AEs and the relationship to investigational product will be summarized for each System Organ Class and Preferred Term by treatment group.

Withdrawals because of AEs will be summarized for each body system and Preferred Term by treatment group.

As described in Section 11.2, TEAEs are defined as those AEs that develop or worsen after the first dose of study medication up to and including the safety follow-up assessment 30 days after the last dose of study drug (up to Study Day 51 with a +7-day window).

AE summaries will be presented across all subjects. All AEs will be listed by subject, along with information regarding onset, duration, relationship, and severity to investigational product, action taken with investigational product, treatment of event, and outcome.

All laboratory assessments will be summarized by treatment group using appropriate descriptive statistics.

Changes from baseline in clinical laboratory tests will be summarized, using descriptive statistics, by visit and nominal time after dosing, and by treatment group. Baseline will be taken as the last predose assessment. Out-of-range values will be flagged in data listings.

Changes from baseline in vital signs will be summarized, using descriptive statistics, by treatment, visit, and nominal time after dosing. Baseline will be taken as the last predose assessment.

Values of potential clinical significance will be flagged in listings and summarized by treatment.

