7.1 Adverse Events

Adverse events (AEs) will be coded using the most recent version of MedDRA (version 23.0). Adverse event severity level will be classified into mild, moderate, severe by investigators. For incidence summaries, a missing severity of an AE will be conservatively imputed as severe. Handling rules for missing severity of AEs are described in Section 12.6.5.

AEs are classified as related to study drug if AEs are definitely or possibly related to study drug. Any AEs with missing or unknown relationship will be considered as related to study drug (Section 12.6.6).

Treatment emergent adverse events (TEAEs) are defined as those AEs that develop or worsen in severity after the first dose of study drug and up to 30 (+7) days beyond the last dose of study drug.

All summaries of AEs described in this section will be on TEAEs. An overall summary of the number of subjects with TEAEs as well as the total number of events will be presented, including the number and percentage of subjects with

- any TEAEs,
- treatment-emergent serious adverse events (SAEs),
- treatment-related TEAEs,
- treatment-related SAEs,
- infusion site reaction TEAEs,

Clinical Protocol APL9-COV-201

Apellis Pharmaceutical, Inc Statistical Analysis Plan V2.0

- TEAEs leading to dose modification (dose reduction or interruption),
- TEAEs leading to treatment discontinuation,
- TEAEs leading to study discontinuation,
- TEAEs leading to death.

The number and percentage of patients reporting TEAEs will be tabulated by SOC and PT; by SOC, PT, and maximum severity.

In summary, the following types of tables will also be provided:

- TEAEs by SOC and PT
- TEAEs by SOC, PT and maximum severity
- Treatment-emergent SAEs by SOC and PT
- Treatment-related TEAEs by SOC and PT
- Treatment-related SAEs by SOC and PT
- Infusion site reaction TEAEs by SOC and PT
- TEAEs leading to dose modification by SOC and PT
- TEAEs leading to treatment discontinuation by SOC and PT
- TEAEs leading to study discontinuation by SOC and PT
- TEAEs leading to death by SOC and PT

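### SAP 7.1 shows the primary TEAE/SAE endpoint only over the whole 30 (+7)-day window; adding a by-arm table by onset period would be a cheap improvement

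*Protocol*

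**What the plan says.** Protocol 7.3 describes a regimen meant to keep complement suppressed while the infusion runs, and then says: "Discontinuation of dosing is expected to restore normal complement activity within 24 hours". Among the risks, Protocol 5.3 lists "possible increased risk of bacterial infection due to complement inhibition".

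The primary objective is safety against vehicle (Protocol 6.1.1). The primary endpoint is the cumulative incidence of TEAEs and treatment-emergent SAEs (Protocol 6.2.1). Protocol 12.4 runs the treatment-emergent window "up to and including the safety follow-up assessment 30 days after the last dose of study drug", with an outer limit of Study Day 51 (+7). SAP 7.1 counts events that develop or worsen "after the first dose of study drug and up to 30 (+7) days beyond the last dose of study drug".

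For Part 2 the basic course in Protocol 7.1 is stated as "Subjects will receive treatment with APL-9 or vehicle from Day 1 through Day 7", followed by alternative end points of which the latest applies. The DMC may approve extension up to Day 21 for qualifying subjects.

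SAP 7.1 bases every AE summary on TEAEs as defined over the whole window. Its table list has no split by onset period, no exposure-adjusted rate and no time-to-first-event display. Protocol 11.2.4 has the onset date and time and the relation to dosing recorded for each event, and Protocol 12.4 plans a by-subject listing that includes onset.

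**The concern.** By the protocol's own account, the pharmacological effect is present during infusion and for about a day afterwards. The only by-arm comparison of the primary endpoint adds about a month of later follow-up in seriously ill patients. Events in that month that have nothing to do with study drug raise both arms alike. If APL-9 causes an excess only while it is being given, the two whole-window percentages lie closer together than those for the on-drug period, and any TEAE may approach its ceiling in both arms. This happens even when both arms are treated for exactly the same time.

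With about 30 subjects per arm and a descriptive safety comparison, the reader relies on the contrast shown in the tables. A table by onset period drawn up after unblinding would be post hoc; prespecifying it avoids that.

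**Working it through.** **The plan's own figure.** Protocol 12.1 and SAP 3.2 give the chance of at least one SAE in an arm of 30. From 1 - (1 - p)^30, p = 1%, 4%, 7% and 10% give 26.0%, 70.6%, 88.7% and 95.8%. These match the stated 26%, 71%, 89% and above 95%, and nothing below changes them.

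**Share of the window off drug.** Let T be treatment days and w the follow-up allowance (0 or 7 days), and count the 24-hour recovery as on drug. The off-drug share is (29 + w)/(T + 30 + w).
- T = 7: 29/37 = 78.4%; with +7, 36/44 = 81.8%.
- T = 21: 29/51 = 56.9%; with +7, 36/58 = 62.1%.

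These are full windows; death or loss to follow-up shortens the off-drug part.

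**What this does to the comparison.** The documents give neither a background SAE rate nor event timing, so both are assumptions here. Let H = -ln(1 - background risk) be the cumulative background hazard over 37 days, f the share of H falling in Days 1-8, and m the hazard multiplier while on drug.
- Days 1-8: vehicle 1 - exp(-fH); APL-9 1 - exp(-m f H).
- Whole window: vehicle 1 - exp(-H); APL-9 1 - exp(-[H + (m - 1) f H]).

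For a 30% background, H = 0.3567. A constant hazard means f = 8/37 = 21.6%, so fH = 0.0771. Results (APL-9 v vehicle):

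| m | f | Days 1-8 | Ratio | Whole window | Ratio |
|---|---|---|---|---|---|
| 2 | 21.6% | 14.3% v 7.4% | 1.93 | 35.2% v 30% | 1.17 |
| 2 | 50% | 30.0% v 16.3% | 1.84 | 41.4% v 30% | 1.38 |
| 2 | 70% | 39.3% v 22.1% | 1.78 | 45.5% v 30% | 1.52 |
| 3 | 21.6% | 20.7% v 7.4% | 2.78 | 40.0% v 30% | 1.33 |
| 3 | 50% | 41.4% v 16.3% | 2.54 | 51.0% v 30% | 1.70 |
| 3 | 70% | 52.7% v 22.1% | 2.39 | 57.5% v 30% | 1.92 |

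Under this model the risk difference shrinks by a known factor: the whole-window difference equals the Day 1-8 difference times exp(-(1 - f)H), the background chance of staying event-free in the off-drug period. For m = 2 and constant hazard that is 6.9 points × 0.756 = 5.2 points. The ratio therefore shrinks much more than the difference.

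Over 24 combinations (background 20%, 30%, 40% or 60%; m = 2 or 3; f = 21.6%, 50% or 70%), both the ratio and the risk difference were larger in Days 1-8 every time.

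**Power, for illustration only.** The SAP plans no AE test. With Fisher's exact test, 30 per arm, two-sided 10%, a 30% background and constant hazard, power in Days 1-8 against the whole window is 9% v 8% for m = 2 and 27% v 14% for m = 3. At a 20% background with m = 2 it is 4% v 6%. That reversal reflects the conservatism of the exact test at very small counts; the risk difference is still larger in Days 1-8 (4.5 v 3.8 points).

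**The case against.** The strongest counter-argument is that recovery of complement activity does not end clinical risk. An infection acquired under inhibition can surface days later, and Protocol 5.3 also allows for unknown effects. Appendix 3 shows that Amendment 1 lengthened safety follow-up from 7 to 30 days, so the long window is deliberate. For the named risk, subjects in both arms receive broad-spectrum antibiotics during treatment (Protocol 9.5), so the on-drug days are also the antibiotic-covered days. All of this stands. It is why the whole window should remain the primary display and why Days 1-8 should not be called the at-risk period.

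Second, the 10% tests belong to the efficacy sections (Protocol 12.3, SAP 6), and AE analysis is descriptive. That also stands, so no claim about lost power in a planned test can be made.

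Third, some tables are already linked to dosing: treatment-related events, infusion site reactions, and events leading to dose modification or treatment discontinuation. Onset appears in the listings, and the DMC sees unblinded tables under a separate analysis plan (SAP 11) that is not available here. This stands in part. Relatedness is an investigator's judgement rather than a time window, a by-subject listing is not a by-arm comparison, and DMC tables are not the final analysis.

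Fourth, if background events cluster early, as is plausible in hospital, the attenuation is milder. The table shows this: at f = 70% and m = 2 the ratios are 1.52 and 1.78.

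**Conclusion.** This is a worthwhile, inexpensive addition to the primary safety analysis, not an error. No statement in the plan is contradicted, and no sample size or stated probability changes.

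The attenuation is real on one condition: that an excess is confined to the on-drug period. Its size depends on an assumed background risk, hazard multiplier and event timing. At a 30% background the whole-window ratio is 1.17-1.52 against 1.78-1.93 in Days 1-8 for a doubled hazard, and 1.33-1.92 against 2.39-2.78 for a tripled one.

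A reader might infer that about 80% of a safety signal is lost. The documents do not support that: the figure is a share of calendar time, applies to a 7-day course only, and says nothing about when events occur. A reader might also infer that drug risk ends on Day 8, or that the 30 (+7)-day window is a mistake. Protocol 7.3 speaks only of complement activity, and late-surfacing events are a good reason for the long window.

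**What to change.** In SAP 7.1, keep the 30 (+7)-day window as the primary display. Prespecify a supplementary by-arm display of any TEAE, any treatment-emergent SAE, and the SOC/PT table (including infections) by onset period: Days 1-8 and after. Days 1-8 is the 7-day course plus the 24 hours in Protocol 7.3. Being fixed, the window is the same for every subject and does not depend on how long anyone was treated.

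If dosing is extended, also show events from first dose to last dose + 1 day, with exposure-adjusted rates, because that window differs between subjects and the fixed one omits later on-drug days.

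The cost is SAP wording and one more set of descriptive tables from onset data already collected; conduct and data collection are unchanged. The downsides are smaller counts per cell, and that events caused on drug but appearing later fall outside the on-drug column. The second is why the new tables supplement the whole-window display and do not replace it.

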# 7.4. End of Study Definition

A subject is considered to have completed the study if all obtainable study assessments, including those at the day of discharge from the hospital and during follow-up, have been collected.

The end of the study is defined as the date of the safety follow-up assessment 30 days after the last dose of study drug (up to and including Study Day 51 with a +7-day window) for the last subject in the study.

[figure not shown]
## 7.5. Study Design and Schedule of Assessments

## Figure 1: Study Schema—Part 1

Abbreviations: ARDS = acute respiratory distress syndrome; AEs = adverse events; DMC = data monitoring committee; PaO2 = partial pressure of oxygen; SAEs = serious adverse events; SOC = standard of care.

## Figure 2: Study Schema—Part 2

Abbreviations: ABG = arterial blood gas; DMC = data monitoring committee;  $FiO_2$  = fraction of inspired oxygen;  $PaO_2$  = partial pressure of oxygen; PI = primary investigator; SOC = standard of care.

## Table 1:Schedule of Assessments

	Study Day(s) a													
	Part 1 and Part 2 a								Pa	art 2 onl	y a	Part 1 and Part 2 a		
List of activities/assessments	Screening/baseline —7 to 1 b	2	3	4	5	6	7	8-10	11	12-14	15	16-21	EOT and discharge day a,n	Safety follow- up assessment a Up to and including Study Day 51 (+7)
Informed consent b	Х													
Inclusion/exclusion b	Х													
SARS-CoV-2 confirmation c	Х													
Medical history 	Х													
Demographics	Х													
eGFR/ALT	Х													
Serum pregnancy test	Х													
Height/body weight/BMI d	Х													
Randomization (Part 2 only)	Х													
Study drug administration a	Х	Х	Х	Х	Х	Х	Χ	Х	X	X	Х	Х	Х	
Discharge card dispensation e													Х	
SAFETY ASSESSMENTS														
Vital signs f	Х	Х	Х	Х		Х	Χ	Х	X	X	Х	Х	Х	
ECG f	Х	Х	Х	Х		Х	Χ	Х	X	X	Х	Х	Х	
SOFA score g	Х		Х		Х		Χ		X		Х		Х	
Clinical laboratory tests h	Х		Х		Х		Χ		X		Х		Х	
Viral RNA or viral antigen assessment k	Х						Χ				Х		Х	
Radiograph/CT scan (pulmonary consolidation)	Х						Χ						Х	
Concomitant medications and procedures i	Х	Χ	Х	Х		Х	Χ	Х	X	X	Х	X	Х	Х
Infusion site reactions j	Х	Х	Х	Х		Х	Χ	Х	X	X	Х	Х	Х	Х
Adverse events	Х	Х	Х	Х	Х	Х	Χ	Х	X	X	Х	X	Х	Х
PHARMACODYNAMIC AND PHARMACOKINETIC ASSESSMENTS														
PK (APL-9)/PD (complement, coagulation, and inflammation)	X		Х		X		Х		Х		Х		$X^{m}$	

Abbreviations: ABG = arterial blood gas; AE = adverse event; ALT = alanine aminotransferase; ARDS = acute respiratory distress syndrome; BMI = body mass index; CT = computed tomographic; DMC = data monitoring committee; ECG = electrocardiogram; eGFR = estimated glomerular filtration rate; EOT = endof-treatment visit;  $FiO_2$  = fraction of inspired oxygen; GCS = Glasgow Coma Scale; ICU = intensive care unit;  $PaO_2$  = partial pressure of oxygen; PD = pharmacodynamics; PK = pharmacokinetics; SAE = serious adverse event; SARS-CoV-2 = severe acute respiratory syndrome coronavirus 2; SOFA = Sequential Organ Failure Assessment;  $SpO_2$  = peripheral oxygen saturation.

Apellis Pharmaceuticals, Inc

#### APL-9 APL9-COV-201 Protocol Amendment 3

- a Dosing must occur on Day 1, on the same day as randomization. The duration of subject participation in this trial may be variable. In Part 1, subjects may receive open-label treatment through Day 7 or resolution of ARDS (whichever occurs earlier). A DMC will review safety data from Part 1 and determine whether Part 2 can be initiated and whether Part 2 treatment can be extended beyond Day 7. Required criteria for initiation of Part 2 will include (1) no fatal/life-threatening SAEs thought possibly related to APL-9 by the DMC, and (2) no more than 1 subject requiring premature treatment discontinuation by the investigator due to AEs or abnormal laboratory tests. In Part 2, dosing may be extended only in subjects who still require respiratory support (oxygen supplementation or mechanical ventilation) at Day 7 with an improved PaO2/FiO2 ratio of at least 20 mm Hg from baseline if ABG test results are available for comparison. If ABG test results are not available, an improvement of FiO2 of at least 4% in nonventilated subjects (eg, those on nasal cannula) and 10% in mechanically ventilated subjects is needed. FiO2 should be weaned following the site's protocol to keep oxygen saturation at 89% or above. Treatment beyond Day 7 and through any DMC-approved extension will be at the discretion of the investigator. In Part 2, subjects will receive treatment up to and including the DMC-approved treatment duration, discontinuation of respiratory support (oxygen supplementation or mechanical ventilation), or hospital discharge (whichever occurs latest). Through Part 2, the DMC may review efficacy and safety data and recommend changes to the study conduct on an ongoing basis, but it will be required to review efficacy and safety data after the 10th and 30th subjects reach the DMC-approved treatment duration, discontinuation of respiratory support, or hospital discharge (whichever occurs latest). Enrollment will not be suspended during the DMC reviews. Subjects who reach the end of the approved treatment duration, discontinuation of respiratory support, or hospital discharge (whichever occurs latest) must be assessed as indicated in the EOT and discharge day column (for example, a subject who reaches the end of the approved treatment and achieves discontinuation of respiratory support on Day 6 should be evaluated with a radiograph or CT scan even though it is not indicated as a Day 6 assessment). All subjects will be followed up at the safety follow-up assessment 30 days after last study treatment (up to and including Study Day 51 with a +7-day window), either in person (for subjects still hospitalized) or by phone (for subjects who have been discharged).
- b Fully eligible subjects can have screening assessments on the same day as baseline, which is defined as the day of initial study drug treatment.
- c Confirmation of SARS-CoV-2 infection may be completed more than 7 days before baseline. Presence of SARS-CoV-2 viral RNA or viral antigen may be detected in respiratory specimens (collected using nasopharyngeal or oropharyngeal swabs) with a qualitative nucleic acid amplification test (such as reverse transcriptase polymerase chain reaction), viral antigen test, or other diagnostic method that is authorized, cleared, or approved by the US Food and Drug Administration or equivalent authority for SARS-CoV-2 viral detection. Note: Serology-based antibody tests do not detect presence of virus and therefore are not considered diagnostic for active infection and cannot be used for study eligibility screening or for subsequent SARS-CoV-2 assessments.
- d Height/weight can be by subject assertion.
- e Discharged subjects who are followed up by phone will be provided with emergency study cards that include a list of symptoms associated with infections. The study card also guides subjects with instructions to contact their study physicians or seek emergency medical care if they experience any of the listed symptoms.
- f For continuous variables, the worst observed daily value will be recorded. Vital signs and ECG must be collected between the administration of the loading dose of study treatment and the initiation of the maintenance dose.
- g SOFA score variables (PaO2/FiO2 ratio or SpO2/FiO2 ratio, platelets, bilirubin, hypotension/vasopressor use, GCS score, creatinine) are detailed in Section 11.1.1 and Appendix 1.
- h A list of laboratory assessments is provided in Section 11.1.8. Blood will be collected 3 times on Day 1: (1) once prior to administration of the APL-9 bolus, (2) once as soon as possible following the bolus (within 5-10 minutes) prior to the continuous infusion, and (3) once at 2 hours after the beginning of the continuous infusion. Following that, assessments should be collected within the time frame of each calendar day. The use of silica reagents in coagulation panels should be avoided in subjects treated with APL-9.
- i The concomitant procedures include recording the day that the subject was admitted to the ICU (or ICU-type environment), use of ventilatory support, use of oxygen therapy, date of ICU discharge, date of hospital discharge, and survival. The time and date of any changes to concomitant medications and procedures are to be recorded at the days indicated in the schedule of assessments. In case of early hospital discharge, the data is collected via phone interviews.

#### APL-9 APL9-COV-201 Protocol Amendment 3

- j Infusion-related reactions that occur during the administration of the 50-mL loading dose should be treated as follows: For mild infusion-related reactions: The 50-mL bag infusion time should be increased from 10 min to 20-40 min and the reaction should be monitored. Treatment with diphenhydramine may be required. The infusion time of the 250-mL bag should not be increased. For severe or persistent mild infusion-related reactions (instances in which the subject's symptoms do not respond to the increased infusion time), treatment should be discontinued, and the institution's emergency hypersensitivity protocol should be employed. Refer to the procedure for handling infusion-related reactions in Section 9.1.1.
- k Confirmation of SARS-CoV-2 infection for screening may be completed more than 7 days before baseline.
-  Vaccination history should be attempted to be collected as a component of medical history.
- m A PK/PD assessment will be done on the last day of treatment. If EOT and discharge day visit are on different days, a PK/PD sample will be collected on the discharge day as an unscheduled visit.
- n If EOT and day of discharge visit are on different days, perform EOT assessments on the last day of treatment and repeat on the day of discharge as an unscheduled visit. Perform/record vital signs, ECG, concomitant medications/procedures, infusion site reactions, and AEs daily up to and including day of discharge. After EOT, record as unscheduled visits.

